7.4.1.2. Method of Detecting AEs and SAEs

Care will be taken not to introduce bias when detecting AEs and/or SAEs. Open-ended and non-leading verbal questioning of the subject is the preferred method to inquire about AE occurrence. Appropriate questions include:

- “How are you feeling?”
- “Have you had any (other) medical problems since your last visit/contact?”
- “Have you taken any new medicines, other than those provided in this study, since your last visit/contact?”

7.4.1.3. Follow-up of AEs and SAEs

After the initial AE/SAE report, the investigator is required to proactively follow each subject at subsequent visits/contacts. All SAEs, and non-serious AEs of special interest (as defined in Section 4.6.1) will be followed until resolution, until the condition stabilizes, until the event is otherwise explained, or until the subject is lost to follow-up (as defined in Section 5.5). Further information on follow-up procedures is given in [Appendix 6](#).

7.4.1.4. Cardiovascular and Death Events

For any cardiovascular events detailed in [Appendix 6](#) and all deaths, whether or not they are considered SAEs, specific CV and Death sections of the eCRF will be required to be completed. These sections include questions regarding cardiovascular (including sudden cardiac death) and non-cardiovascular death.

The CV eCRFs are presented as queries in response to reporting of certain CV Medical Dictionary for Regulatory Activities (MedDRA) terms. The CV information should be recorded in the specific cardiovascular section of the eCRF within one week of receipt of a CV Event data query prompting its completion.

The Death eCRF is provided immediately after the occurrence or outcome of death is reported. Initial and follow-up reports regarding death must be completed within one week of when the death is reported.

7.4.1.5. AEs of Special Interest

In the Phase 3a clinical development program, AEs of special interest included several areas of safety related concern for the T2DM population, particularly for a GLP-1R agonist such as albiglutide.

Specific eCRF pages will be used to capture additional details for the following AEs of special interest:

- Hypoglycemic events (see Section [7.4.9](#))
- Liver events
- CV events (see Section [7.4.1.4](#))
- Injection site reactions
- Potential systemic allergic reactions
- Pancreatitis
- MTC
- Diabetic retinopathy
- Pneumonia
- Atrial fibrillation/atrial flutter

The following additional AEs of special interest will be captured in the AE eCRF pages:

- GI events
- Pancreatic cancer
- Malignant neoplasms
- Appendicitis

Subjects with pancreatitis, MTC or any drug hypersensitivity reaction, that is not reasonably attributable to another cause, should be withdrawn from the study and should not be rechallenged with albiglutide or exenatide (see Section 5.5 for complete list of AEs of special interest requiring withdrawal).

If a histopathologic analysis related to events of special interest is performed, a copy of the histopathology report and a discharge summary if the subject was admitted, or any available case summary (e.g. clinic letter), is to be provided to the Sponsor, if available.

Subjects with treatment emergent thyroid nodules should be referred to a specialist for evaluation in accordance with local treatment guidelines.

Subjects will be provided information detailing the symptoms of pancreatitis and will be instructed to hold study medication and contact the investigator immediately if they experience any of these symptoms. All cases of suspected pancreatitis will be referred to the PAC (see Section 10.8.1).

Subjects should also be closely monitored for signs of potential allergic or drug hypersensitivity reactions including anaphylaxis, angioedema, generalized urticaria, and other potential manifestations of systemic allergic or drug hypersensitivity reactions. A serum sample should be taken as soon as possible after any such event in order to measure antibody to the drug. Instructions for sample processing are provided in Section 7.6. These events should be reported as AEs or SAEs based on the clinical evaluation of the subject.

7.4.1.6. Regulatory Reporting Requirements for SAEs

Prompt notification by the investigator to GSK of SAEs related to study treatment (even for non- interventional post-marketing studies) is essential so that legal obligations and ethical responsibilities towards the safety of subjects and the safety of a product under clinical investigation are met.

GSK has a legal responsibility to notify both the local regulatory authority and other regulatory agencies about the safety of a product under clinical investigation. GSK will comply with country specific regulatory requirements relating to safety reporting to the regulatory authority, Institutional Review Board (IRB)/Independent Ethics Committee (IEC) and investigators.

Investigator safety reports are prepared for suspected unexpected serious adverse reactions according to local regulatory requirements and GSK policy and are forwarded to investigators as necessary.

An investigator who receives an investigator safety report describing a SAE(s) or other specific safety information (e.g., summary or listing of SAEs) from GSK will file it with the IB and will notify the IRB/IEC, if appropriate according to local requirements.

7.4.2. Pregnancy

- If a subject becomes pregnant during the study they should discontinue Investigational Product.
- Any pregnancy that occurs during study participation (i.e., from baseline/randomization through the end of the post-treatment follow-up period) must be reported using a clinical trial pregnancy form.
- If a pregnancy is reported then the investigator should inform GSK or designee within 2 weeks of learning of the pregnancy and should follow the procedures outlined in [Appendix 4](#).

7.4.3. Physical Exams

A full or brief physical examination will be performed at the time points specified in the Time and Events Table Section [7.1](#).

- A full physical examination will include, at a minimum, assessment of the skin (including injection site), head, eyes, ears, nose, throat, thyroid, respiratory system, cardiovascular system, abdomen (liver and spleen), lymph nodes, central nervous system and extremities.
- Brief physical examination includes evaluation of skin (including injection site), respiratory system, cardiovascular system, abdomen (liver, spleen), and central nervous system
- Investigators should pay special attention to clinical signs related to previous serious illnesses
- Weight will be performed at the time points specified in the Time and Events Table Section [7.1](#). Height and body mass index will be measured and recorded at screening only. Height and weight should be measured with the subject in indoor daytime clothing with no shoes.

7.4.4. Vital Signs

For vital signs (blood pressure and pulse rate), a single measurement will be taken at the time points specified in the Time and Events Table (Section [7.1](#))

During visits when ECGs are scheduled, vital sign measurements will be taken after the completion of the ECG sampling. Subjects may be either in a semi-recumbent or seated position. During visits when ECGs are not scheduled, vital sign measurements will be taken while subjects are in a seated position after at least a 5-minute rest period. During visits where a blood draw is required, vital sign measurements will be taken prior to sample collection.

7.4.5. Electrocardiogram (ECG)

[figure not shown]
A single 12-lead ECG recording (with subject in semirecumbent position for 10 to 15 minutes before obtaining the ECG) will be performed at screening only using an ECG

machine that automatically calculates the heart rate and measures PR, QRS, QT, and QTc intervals.

[figure not shown]
It is recommended that the ECGs be performed **before** measurement of vital signs and collection of blood samples for laboratory testing.

7.4.6. Gastroparesis Cardinal Symptom Index Daily Diary (GCSI-DD)

CCI - This section contained Clinical Outcome Assessment data collection questionnaires or indices, which are protected by third party copyright laws and therefore have been excluded.

CCI - This section contained Clinical Outcome Assessment data collection questionnaires or indices, which are protected by third party copyright laws and therefore have been excluded.

7.4.7. Clinical Safety Laboratory Assessments

All protocol required laboratory assessments, as defined in [Table 4](#), must be conducted in accordance with the Laboratory Manual, and Protocol Time and Events Schedule.

Laboratory requisition forms must be completed and samples must be clearly labeled with the subject number, protocol number, site/centre number, and visit date. Details for the preparation and shipment of samples will be provided by the laboratory and are detailed laboratory manual. Reference ranges for all safety parameters will be provided to the site by the laboratory responsible for the assessments.

If additional non-protocol specified laboratory assessments are performed at the institution's local laboratory and result in a change in subject management or are considered clinically significant by the investigator (e.g., SAE or AE or dose modification) the results must be recorded in the eCRF.

Refer to the SRM for appropriate processing and handling of samples to avoid duplicate and/or additional blood draws.

All study-required laboratory assessments will be performed by a central laboratory with the exception of the fasting capillary blood glucose as noted in the Time and Events Table.

Hematology, clinical chemistry, urinalysis and additional parameters to be tested are listed in [Table 4](#). Prior to the collection of blood samples, subjects should be **fasting** [no food or drink (except water) for at least 8 hours before sample collection]. During visits where ECGs and vital sign measurements are scheduled, blood samples will be collected after the completion of these assessments.

Table 4 Protocol Required Laboratory Assessments

Laboratory Assessments	Parameters		
Hematology	
 • Platelet count • RBC count • Hemoglobin • Hematocrit 	
 • WBC count with Differential • Neutrophils • Lymphocytes • Monocytes • Eosinophils • Basophils 	
Clinical Chemistry¹	
 • AST • ALT • GGT • BUN • Creatinine • eGRF (MDRD) 	
 • Bilirubin (total and direct/indirect) • Calcium • Magnesium • Potassium • Sodium 	
 • Phosphorous • Chloride • Albumin • Total protein
Urinalysis	
 • Specific gravity • Ketones • Leukocyte esterase • Microscopic examination (if blood or protein is abnormal) 	
 • pH • Blood • Microalbumin 	
 • Glucose • Nitrates • Creatinine
Glycemic parameters	
 • HbA1c 	
 • FPG 	
 • Fasting capillary glucose
Lipid parameters⁵	
 • Total cholesterol • Triglycerides 	
 • LDL-C (direct) 	
 • HDL-C
Other laboratory tests	
 • Serum pregnancy test² • Urine pregnancy test² • Amylase⁶ 	
 • FSH³ • TSH⁴ 	
 • Estradiol³ • Lipase⁶
AST, aspartate transaminase; GGT, γ -glutamyltransferase; LDL-C, low density lipoprotein-C; HDL-C, high density lipoprotein-C; TSH, thyroid stimulating hormone, WBC, white blood cells			
1. Details of Liver Chemistry Stopping Criteria and Required Actions and Follow-Up Assessments after liver stopping or monitoring event are given in Section 5.5.1 and Appendix 5.			
2. For females of reproductive potential only.			
3. As needed in postmenopausal women were their menopausal status is in doubt (see Inclusion Criteria Section 5.1).			
4. TSH screening only. If TSH is above the ULN, free T4 (reflex) will also be measured			
5. Screening only.			
6. Screening only.			

All laboratory tests with values that are considered clinically significantly abnormal during participation in the study or within 25 days after the last dose of study treatment should be repeated until the values return to normal or baseline. If such values do not return to normal within a period judged reasonable by the investigator, the etiology should be identified and the sponsor notified.

7.4.7.1. FPG and HbA_{1c} Central Laboratory

HbA1c and FPG will be measured at the time points specified in the Time and Events Table in Section 7.1. If subjects are scheduled to receive study treatment during an in-clinic visit, blood samples for HbA1c and FPG should be collected before administration of study treatment.

7.4.7.2. Estimated Glomerular Filtration Rate (eGFR)

In order to monitor kidney function, serum creatinine will be measured at the time points specified in Time and Events Schedule in Section 7.1. It will be used to calculate eGFR using the MDRD formula [Levey, 2009], namely:

$$\text{eGFR (ml/min/1.73m2)} = 175 \times (\text{serum creatinine})^{-1.154} \times (\text{Age})^{-0.203} \times (0.742 \text{ if female}) \times (1.212 \text{ if African American}).$$

7.4.8. Diabetic Dietary Instruction and Exercise

Standard diabetic dietary and exercise guidance will be provided by the site at screening and reinforced at each study visit specified in the Time and Events Table in Section 7.1.

7.4.9. Home Blood Glucose Monitoring

Home blood glucose monitoring advice as well as advice on the signs and symptoms of hypoglycemia will be provided by the site at screening and reinforced at each study site visit specified in the Time and Events Table in Section 7.1.

All subjects in the study will be recommended to measure and record/store blood glucose values using their glucose meter each morning before breakfast. At least one day per week, subjects should measure blood glucose values at the following times (except GEBT and EGG assessment days).

- Before breakfast (at least 8 hours without food intake)
- Before lunch
- Before dinner
- At bedtime

The investigator will review the glucose meter readings at each study visit and will decide the frequency of measurements based on the subject's individual needs.

Subjects should monitor the blood glucose as per the instructions of the investigator and as appropriate for their medical management. The subjects should report promptly, as directed by the investigator, the occurrence of hyperglycemia (i.e. fasting capillary blood

glucose >270 mg/dL) or hypoglycemia (particularly if symptomatic) to the investigator (or his or her designee). Assessment and action should then occur as deemed appropriate by the investigator

7.4.9.1. Fasting Capillary Blood Glucose at clinical visits

Capillary blood glucose will be measured prior to the EGG and GEBT procedures and recorded in the eCRF at the time points specified in the Time and Events Schedule in Section 7.1.

7.4.10. Hyperglycemic Events

Subjects will be asked to report any hyperglycemic events, including time between study visits. Subjects requiring rescue therapy due to fasting plasma glucose ≥ 270 mg/dL confirmed by central lab will be withdrawn from the study. At investigator discretion, a subject may be withdrawn for hyperglycemia at any time for safety considerations, not necessarily reaching the threshold of fasting plasma glucose ≥ 270 mg/dL

7.4.11. Hypoglycemic Events

Specific criteria for monitoring hypoglycemic events have been designed to ensure subject safety and to closely monitor hypoglycemia. Hypoglycemic events are defined as follows [Sequist, 2013]:

Severe Hypoglycemia

- Severe hypoglycemia is an event requiring assistance of another person to actively administer carbohydrates, glucagon, or take other corrective actions. Plasma glucose concentrations may not be available during an event, but neurological recovery following the return of plasma glucose to normal is considered sufficient evidence that the event was induced by a low plasma glucose concentration.

Documented Symptomatic Hypoglycemia

- Documented symptomatic hypoglycemia is an event during which typical symptoms of hypoglycemia are accompanied by a measured plasma glucose concentration ≤ 70 mg/dL (≤ 3.9 mmol/L).

Asymptomatic Hypoglycemia

- Asymptomatic hypoglycemia is an event not accompanied by typical symptoms of hypoglycemia but with a measured plasma glucose concentration ≤ 70 mg/dL (≤ 3.9 mmol/L).

Probable Symptomatic Hypoglycemia

- Probable symptomatic hypoglycemia is an event during which symptoms typical of hypoglycemia are not accompanied by a plasma glucose determination but that was presumably caused by a plasma glucose concentration ≤ 70 mg/dL (≤ 3.9 mmol/L).

Pseudohypoglycemia

- Pseudohypoglycemia is an event during which the person with diabetes reports any of the typical symptoms of hypoglycemia with a measured plasma glucose concentration >70 mg/dL (>3.9 mmol/L) but approaching that level.

Any hypoglycemic event, regardless of intensity, that satisfies the definition of an SAE ([Appendix 6](#)) should be categorized as outlined in this section and reported appropriately in the SAE eCRF page and the hypoglycemic events AE of special interest page.

7.5. Tracking of Albiglutide and Exenatide Pen Injector Failures and User Errors

All albiglutide pen injector failures and user errors must be detected, documented, and reported by the investigator throughout the study. Detailed information on albiglutide pen injector failures and user errors will be collected on the Albiglutide Injector Pen and Reporting Form.

For both, albiglutide and exenatide pen injector failures and user errors associated with or resulting in events fulfilling the definition of an AE or SAE will follow the processes outlined in Section [7.4.1](#).

7.6. Immunogenicity

In the case of severe systemic allergic reactions that include anaphylaxis, angioedema, or other severe potential hypersensitivity reactions in subjects that have received albiglutide, that cannot reasonably be attributed to another cause, three 1-mL serum samples should be obtained for immunogenicity testing (within 24 hours of the event if possible) and sent to the central laboratory (see details in the SRM) for immediate distribution to contracted testing facility for specific immunological testing (albiglutide-specific immunoglobulin E and other tests, as appropriate). A follow-up serum sample will be taken 8 weeks after final dose of study treatment in these subjects.

Subjects with drug hypersensitivity reactions that are not reasonably attributable to another cause should be withdrawn from the study and should not be rechallenged with albiglutide (see Section [5.5](#) and Section [7.4.1.5](#)).

7.7. Genetics

Information regarding genetic research is included in [Appendix 7](#).

8. DATA MANAGEMENT

- For this study, subject data will be entered into GSK defined eCRFs, transmitted electronically to GSK or designee and combined with data provided from other sources in a validated data system.
- Management of clinical data will be performed in accordance with applicable GSK standards and data cleaning procedures to ensure the integrity of the data, e.g., removing errors and inconsistencies in the data.
- AEs and concomitant medications terms will be coded using MedDRA and an internal validated medication dictionary, GSKDrug.
- eCRFs (including queries and audit trails) will be sent at the end of the study in CD format to GSK to be retained. Each investigator will receive a copy of their site specific data in the same format to maintain as the investigator copy. Subject initials will not be collected or transmitted to GSK according to GSK policy.

9. STATISTICAL CONSIDERATIONS AND DATA ANALYSES

9.1. Part A: Statistical Considerations and Data

9.1.1. Hypotheses

No formal statistical hypotheses are being tested in Part A. Part A will be a pilot phase investigating the effect of repeated doses of exenatide on GMA, GE, and VAS of nausea.

9.1.2. Sample Size Considerations

9.1.2.1. Sample Size Assumptions

Sample size for Part A is not based on formal sample size calculations; it is based on the anticipated minimum number to better estimate the effect of repeated doses of exenatide on GMA. The pivotal assessment of the repeated doses on GMA will be provided by Part B of the study, with Part A providing an exploratory assessment to support progression to Part B.

Approximately 10 evaluable subjects with T2DM will be enrolled in Part A of the study.

9.1.2.2. Sample Size Re-estimation or Adjustment

If subjects prematurely discontinue the Part A of the study or if the central data reader reports that the data is not valid, additional replacement subjects maybe enrolled at the discretion of the Investigator in consultation with the Sponsor.

9.1.3. Data Analysis Considerations

All protocol defined endpoints will be summarized using suitable displays.

9.1.3.1. Analysis Populations

For this exploratory study, the analysis set will include subjects who have valid data. Data will be assessed and reviewed by the central reader before it is considered valid. Additional details will be provided in the RAP.

9.1.4. Key Elements of Analysis Plan

9.1.4.1. Exploratory Analysis

No formal statistical analyses will be performed for the exploratory endpoints that are listed under Section 3.1. All exploratory endpoints will be assessed using descriptive statistics and graphical displays as appropriate.

9.1.4.2. Part A review

Changes resulting from Part A review including refinement of endpoints and statistical assessment of the endpoints will be incorporated in the RAP and will not be considered an amendment to the Protocol

9.2. Part B: Statistical Considerations and Data Analysis

9.2.1. Hypotheses

Hypotheses testing in Part B will be performed for the parameters listed in Section 3.2 to compare albiglutide to exenatide in subjects with T2DM for a treatment period of 8 weeks.

9.2.2. Sample Size Considerations

9.2.2.1. Sample Size Assumptions

Approximately 62 subjects (31 per arm) will be randomized in a 1:1 ratio to either albiglutide or exenatide. The study will target to have a total of approximately 50 evaluable subjects (25 subject per treatment arm) taking into account the assumed withdrawal rate of approximately 20%. The study is exploratory in nature and there is no similar published work available in the same indication and population to act as a guide. This sample size is based on feasibility and the sample size assumptions may be re-evaluated once Part A results are available.

9.2.2.2. Sample Size Re-estimation or Adjustment

Based on the results from Part A the total sample size for Part B may be adjusted, within the bounds of feasibility.

9.2.3. Data Analysis Considerations

9.2.3.1. Analysis Populations

For this exploratory study, the analysis set will include subjects who have valid data. Data will be assessed and reviewed by the central reader before it is considered valid. Additional details will be provided in the RAP.

9.2.3.2. Interim Analysis

This is an open-label exploratory study with sample-size based on feasibility considerations. To support monitoring of endpoint variability; data aggregated by treatment group may be reviewed by the Sponsor while the trial is ongoing.

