6.4. Blinding

This will be a treatment open-label study.

The reviewers/readers of EGG and individuals who perform sample testing and data production for GEBT will be blinded to randomized treatments. The study team will remain blinded to the treatment assigned group for the assessment of safety aggregate data. If an interim analysis is conducted (see Section 9.2.3.2.), the study team may be unblinded to the aggregate data.

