9.2.4. Key Elements of Analysis Plan

9.2.4.1. Primary Analysis

The primary endpoint is change from baseline in EGG parameters at Week 2, 5, and 8 at each time interval (pre-and 10, 20 and 30 min after water load). The primary endpoint is change in GMA as assessed by EGG parameters: change from baseline of distribution of average power by frequency region (as % of power); change from baseline of ratios of average power post-water load test (post-WLT)/pre water load test (pre-WLT) by frequency region; and change from baseline of percentage (%) of time with the dominant EGG frequencies in the four frequency ranges (bradygastria, normal, tachygastria and duodenal). The primary analyses of the primary EGG parameters will be conducted using mixed-effect model with repeated measures (MMRM). The MMRM model will include the EGG parameter as the dependent variable; treatment group, time interval, visit week, and treatment-by-week interaction as fixed effects; the relevant parameter baseline as covariate; and subject as a random effect.

The primary endpoint of change from baseline in EGG parameters related to VAS of nausea at Week 2, 5, and 8 at each time interval (pre-and 10, 20 and 30 min after water load) will be analyzed using the MMRM method as described above. The MMRM model will include the EGG parameter as the dependent variable (the same EGG parameters as listed above); treatment group, time interval, visit week, and treatment-by-week interaction as fixed effects; the relevant parameter baseline as covariate; VAS of nausea as time varying covariate; and subject as a random effect.

Treatment effects estimates (and associated 95% CI) of albiglutide will be evaluated within this MMRM model as least squares means contrasts relative to exenatide. An unstructured covariance matrix will be used for the MMRM analysis, unless the model does not converge, in which case the covariance matrix will be decided upon model convergence status and the Akaike information criterion.

Part B analysis is further described in the RAP.

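### Part B lets the sponsor review data by treatment group to monitor variability, with no limit on content or access and no requirement that the Part B RAP be final first

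*Protocol*

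**What the plan says.** Protocol section 9.2.3.2 (Interim Analysis, Part B) allows one kind of look: "To support monitoring of endpoint variability; data aggregated by treatment group may be reviewed by the Sponsor while the trial is ongoing". It gives no timing, number of looks, list of quantities, list of people with access, or decision that depends on the result.

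Section 6.4 (Blinding) sets the context. Treatment is open-label, but some knowledge is withheld:

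- Test readers: "The reviewers/readers of EGG and individuals who perform sample testing and data production for GEBT will be blinded to randomized treatments".
- Study team: "The study team will remain blinded to the treatment assigned group for the assessment of safety aggregate data".
- Exception: "If an interim analysis is conducted (see Section 9.2.3.2.), the study team may be unblinded to the aggregate data".

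Several Part B analysis matters are deferred to the RAP: details of the analysis set (9.2.3.1), further description of the Part B analysis (9.2.4.1), and further planned analyses including subgroups (9.2.4.3). The protocol sets no date for that RAP relative to the look. The RAP supplied covers Part A only. Its section 3.1 says that no interim analysis is planned, and its section 2.1 records early termination with few subjects enrolled in Part A.

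**The concern.** Section 6.4 treats aggregate results by arm as worth withholding from the study team even though treatment is open-label. It then makes an exception for a review whose stated purpose does not need the arms to be separated.

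Nothing in 9.2.3.2 keeps arm means out of the review. The people who see them may be the people who still have to settle the Part B RAP. Part B tests hypotheses (9.2.1), and its primary endpoint spans several EGG measures, frequency regions, weeks and time intervals (9.2.4.1), so there is room for emphasis to follow the data. If the arm difference is known before the analysis set, additional analyses and subgroups are fixed, a reader of the report cannot tell which of those choices were made independently of the results.

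**Working it through.** **The plan's own figure.** Section 9.2.2.1: "Approximately 62 subjects (31 per arm) will be randomized in a 1:1 ratio to either albiglutide or exenatide", to leave 50 evaluable after about 20% withdrawal. 50 / (1 − 0.20) = 62.5, and 62 × 0.80 = 49.6. The figure reproduces to rounding. No power calculation can be checked, because the documents give no effect size, SD or power; the sample size rests on feasibility.

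**Does monitoring variability need the arms?** Take one endpoint, 1:1 allocation (9.2.2.1) and the same SD, σ, in both arms (assumption). Let d be the true difference divided by σ. Ignoring treatment, the variance is

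σ² + (dσ)²/4,

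so pooled SD / within-arm SD = √(1 + d²/4). The documents give no d, so these values are assumptions:

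| Assumed d | 1 + d²/4 | Ratio | Excess |
|---|---|---|---|
| 0.3 | 1.0225 | 1.011 | 1.1% |
| 0.5 | 1.0625 | 1.031 | 3.1% |
| 0.8 | 1.1600 | 1.077 | 7.7% |
| 1.0 | 1.2500 | 1.118 | 11.8% |

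For comparison, the 95% limits for an SD estimated under normality are √(df/χ²) times the estimate. With 50 subjects (df 49) the multipliers are 0.835 and 1.246. With 25 subjects in total, about half the evaluable data (df 24), they are 0.781 and 1.391. The bias from pooling is smaller than this sampling error over the whole range, and it errs towards a larger SD.

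**What would arm means show?** With n per arm, the 95% half-width for the difference in SD units is 1.96 × √(2/n).

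- n = 12: 0.80
- n = 13: 0.77
- n = 25: 0.55

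At about half the evaluable data, a true difference of 0.8 SD would have an expected z of 0.8 / √(2/12) = 1.96 with 12 per arm, or 2.04 with 13. A large effect would be visible; a moderate one would not be clear (d = 0.5 gives z = 1.22 to 1.27).

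**Does any planned decision use the by-arm result?** Section 9.2.2.2 lets the Part B sample size change on Part A results. Section 4.2 ties other Part B adjustments to the Part A review. No rule refers to the 9.2.3.2 look. The by-arm display therefore has no stated use beyond variability.

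**The case against.** The strongest defence is the nature of the study: "This is an open-label exploratory study with sample-size based on feasibility considerations". The look is disclosed consistently in two sections, and no stopping or sample-size decision depends on it. The phrase in 9.2.3.2 could also mean SDs by arm and nothing else. These points stand as limits on weight. They do not close the gap, because the wording does not exclude means and 6.4 itself describes the result as unblinding.

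A second objection also stands: pooled data cannot show whether spread differs between albiglutide and exenatide, and the formula above assumes that it does not. The protocol does not state that comparison as an aim, but it could be of interest with exenatide as the positive control.

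A reader might infer four stronger things that the documents do not support:

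- *That the primary endpoints could be refined after the look.* Sections 4.2 and 9.1.4.2 tie refinement to the Part A review, and 4.2 places adjustments to Part B before progression to it.
- *That the covariance structure could be chosen to suit the result.* Section 9.2.4.1 starts from unstructured. If that model does not converge, "the covariance matrix will be decided upon model convergence status and the Akaike information criterion". Neither criterion is read from arm means.
- *That blinded reading gives no protection.* Under 9.2.3.1 the central reader judges data validity, and 6.4 blinds EGG readers and GEBT testing staff. That protects the validity decision, though not the later choice of analyses or subgroups.
- *That the type I error rate is inflated.* An unadjusted 5% test at half information plus the final test would give about 8.3%, but the protocol plans no interim test and no efficacy stopping rule.

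**Conclusion.** The concern holds as an access-control and timing gap. Sections 9.2.3.2 and 6.4 permit by-arm aggregate data to reach the study team during Part B without limiting the content, restricting access or requiring the Part B RAP to be final. The choices exposed are those left to that RAP: analysis-set details, further analyses and subgroups.

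The size is modest. It is an operational-bias risk in an open-label exploratory part, with no error-rate consequence in the text as written. Pooling would overstate the SD by about 1% to 12% for assumed d of 0.3 to 1.0, given 1:1 allocation and equal within-arm variances.

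The RAP's statement that no interim analysis is planned does not settle the matter for Part B, because that RAP covers Part A only. As the study ended in Part A, the look could not take place; the point matters if the Part B design is used again.

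**What to change.** 1. In Protocol 9.2.3.2, replace *aggregated by treatment group* with *pooled across treatment groups*.
2. In 6.4, delete the matching sentence that allows the study team to be unblinded to aggregate data.
3. Add that the Part B RAP must be final before any by-arm endpoint summary is produced.

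If a comparison of variability between arms is wanted, state it as an aim and report by-arm SDs without means. In that case do not report the pooled SD beside them: by the formula above, the absolute difference is 2 × √(pooled variance − within-arm variance), so the two together reveal its size.

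The cost is a wording change in each of two sections and a small timing commitment for the RAP. Sample size and alpha are unaffected. What is given up is any view of unequal arm variances, unless the by-arm SD option is taken.
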